8.2 DATA QUALITY ASSURANCE

A risk-based approach is used for trial quality management. It is initiated by the assessment of critical data and processes for trial subject protection and reliability of the results as well as identification and assessment of associated risks. An Integrated Quality and Risk Management Plan documents the rationale and strategies for risk management during trial conduct including monitoring approaches, vendor management and other processes focusing on areas of greatest risk.

Continuous risk review and assessment may lead to adjustments in trial conduct, trial design or monitoring approaches.

A quality assurance audit/inspection of this trial may be conducted by the sponsor, sponsor's designees, or by IRB / IEC or by regulatory authorities. The quality assurance auditor will have access to all medical records, the investigator's trial-related files and correspondence, and the informed consent documentation of this clinical trial.

8.3 RECORDS

CRFs for individual subjects will be provided by the sponsor. For drug accountability, refer to Section [4.1.8](#).

8.3.1 Source documents

In accordance with regulatory requirements, the investigator should prepare and maintain adequate and accurate source documents and trial records for each trial subject that include all observations and other data pertinent to the investigation. Source data as well as reported data should follow the 'ALCOA principles' and be attributable, legible, contemporaneous, original, and accurate. Changes to the data should be traceable (audit trail).

Data reported on the CRF must be consistent with the source data or the discrepancies must be explained.

Before providing any copy of subjects' source documents to the sponsor, the investigator must ensure that all subject identifiers (e.g., subject's name, initials, address, phone number, and social security number) have properly been removed or redacted to ensure subject confidentiality.

If the subject is not compliant with the protocol, any corrective action (e.g. re-training) must be documented in the subject file.

For the CRF, data must be derived from source documents, for example:

- Subject identification: sex, year of birth (in accordance with local laws and regulations)
- Subject participation in the trial (substance, trial number, subject number, date subject was informed)
- Dates of subject's visits, including dispensing of trial medication

Proprietary confidential information © 2018 Boehringer Ingelheim International GmbH or one or more of its affiliated companies

- Medical history (including trial indication and concomitant diseases, if applicable)
- Medication history
- AEs and outcome events (onset date [mandatory], and end date [if available])
- SAEs (onset date [mandatory], and end date [if available])
- Concomitant therapy (start date, changes)
- Originals or copies of laboratory results and other imaging or testing results, with proper documented medical evaluation (in validated electronic format, if available)
- ECG results (original or copies of printouts)
- Completion of subject's participation in the trial (end date; in case of premature discontinuation, document the reason for it, if known)
- Prior to allocation of a subject to a treatment into a clinical trial, there must be documented evidence in the source data (e.g. medical records) that the trial participant meets all inclusion criteria and does not meet any exclusion criteria. The absence of records (either medical records, verbal documented feedback of the subject or testing conducted specific for a protocol) to support inclusion/exclusion criteria does not make the subject eligible for the clinical trial.

8.3.2 Direct access to source data and documents

The investigator /institution will allow site trial-related monitoring, audits, IRB / IEC review and regulatory inspections. Direct access must be provided to the CRF and all source documents/data, including progress notes, copies of laboratory and medical test results, which must be available at all times for review by the Clinical Research Associate, auditor and regulatory inspector (e.g. FDA). They may review all CRFs and informed consents. The accuracy of the data will be verified by direct comparison with the source documents described in Section [8.3.1](#). The sponsor will also monitor compliance with the protocol and GCP.

8.3.3 Storage period of records

Trial site:

The trial site must retain the source and essential documents (including ISF) according to contract or the local requirements valid at the time of the end of the trial (whatever is longer).

Sponsor:

The sponsor must retain the essential documents according to the sponsor's SOPs.

8.4 EXPEDITED REPORTING OF ADVERSE EVENTS

BI is responsible to fulfil their legal and regulatory reporting obligation in accordance with regulatory requirements.

8.5 STATEMENT OF CONFIDENTIALITY AND SUBJECT PRIVACY

Individual subject data obtained as a result of this trial is considered confidential and disclosure to third parties is prohibited with the exceptions noted in Section [8.7](#).

Proprietary confidential information © 2018 Boehringer Ingelheim International GmbH or one or more of its affiliated companies

Data protection and data security measures are implemented for the collection, storage and processing of patient data in accordance with the principles 6 and 12 of the WHO GCP handbook.

Personalised treatment data may be given to the subject's personal physician or to other appropriate medical personnel responsible for the subject's welfare. Data generated at the site as a result of the trial need to be available for inspection on request by the participating physicians, the sponsor's representatives, by the IRB / IEC and the regulatory authorities.

8.5.1 Collection, storage and future use of biological samples and corresponding data

Measures are in place to comply with the applicable rules for the collection, storage and future use of biological samples and clinical data, in particular

- Sample and data usage has to be in accordance with the informed consent
- The BI-internal facilities storing biological samples from clinical trial participants as well as the external storage facility are qualified for the storage of biological samples collected in clinical trials.
- An appropriate sample and data management system, incl. audit trail for clinical data and samples to identify and destroy such samples according to ICF is in place
- A fit for the purpose documentation (biomarker proposal, analysis plan and report) ensures compliant usage
- If applicable, a fit for purpose approach will be used for assay/equipment validation depending on the intended use of the biomarker data

Samples and/or data may be transferred to third parties and other countries as specified in the ICF.

8.6 TRIAL MILESTONES

The **start of the trial** is defined as the date of the enrolment of the first subject in the trial.

The **end of the trial** is defined as the 'date of the last visit of the last subject in whole trial' ('Last Subject Completed') or 'end date of the last open AE' or 'date of the last follow-up test' or 'date of an AE has been decided as sufficiently followed-up', whichever is latest.

Early termination of the trial is defined as the premature termination of the trial for any reason before the end of the trial as specified in this protocol.

Temporary halt of the trial is defined as any unplanned interruption of the trial by the sponsor with the intention to resume it.

Suspension of the trial is defined as an interruption of the trial based on a Health Authority request.

The EC/competent authority in each participating EU member state will be notified about the trial milestones according to the laws of each member state.

A final report of the clinical trial data will be written only after all subjects have completed the trial in all countries (EU or non-EU), so that all data can be incorporated and considered in the report.

Proprietary confidential information © 2018 Boehringer Ingelheim International GmbH or one or more of its affiliated companies

The sponsor will submit to the EU database a summary of the final trial results within one year from the end of a clinical trial as a whole, regardless of the country of the last patient (EU or non-EU).

8.7 ADMINISTRATIVE STRUCTURE OF THE TRIAL

The trial is sponsored by Boehringer Ingelheim (BI).

The trial will be conducted at

, under the supervision of the Principal Investigator. Relevant documentation on the participating (Principal) Investigators (e.g. their curricula vitae) will be filed in the ISF.

BI has appointed a Trial Clinical Monitor, responsible for coordinating all required trial activities, in order to

- Manage the trial in accordance with applicable regulations and internal SOPs
- Direct the clinical trial team in the preparation, conduct, and reporting of the trial
- ensure appropriate training and information of Clinical Trial Manager (CTM), Clinical Research Associates, and investigators of participating trial sites

The non-labelled trial medication (intended commercial formulation (iCF) of 50 mg BI 730357) will be provided by the Clinical Trial Supplies Unit (CTSU), BI Pharma GmbH & Co. KG, Biberach, Germany.

The radio-labelled trial medication (intravenous microtracer solution) will be provided by

Safety laboratory tests will be performed by the local laboratory of the trial site ().

The analyses of unlabelled BI 730357 concentrations in plasma will be performed at the Department of Drug Metabolism and Pharmacokinetics, BI Pharma GmbH & Co. KG, Biberach, Germany.

The analyses of labelled [C-14]BI 730357 BS concentrations in plasma via AMS analysis will be conducted at

On-site monitoring will be performed by BI or a contract research organisation appointed by BI.

Data management and statistical evaluation will be done by BI or a contract research organisation appointed by BI according to BI SOPs.

Tasks and functions assigned in order to organise, manage, and evaluate the trial are defined according to BI SOPs. A list of responsible persons and relevant local information can be found in the ISF.

10. APPENDICES

Not applicable.

Proprietary confidential information © 2018 Boehringer Ingelheim International GmbH or one or more of its affiliated companies

2. LIST OF ABBREVIATIONS

Term	Definition / description
AE	Adverse Event
AESI	Adverse event of special interest
ALT	Alanine aminotransferase
ANOVA	analysis of variance
AST	Aspartate aminotransferase
AUC _{0-∞}	Area under the concentration-time curve of the analyte in plasma over the time interval from 0 extrapolated to infinity
BI	Boehringer Ingelheim
BLQ	Below the lower limit of quantification
BMI	Body mass index
BS	base
CTP	Clinical Trial Protocol
CTR	Clinical Trial Report
DBLM	Database lock meeting
gCV	geometric coefficient of variation
ICH	International Conference On Harmonisation
iPD	Important Protocol Deviations
IQRMP	Integrated Quality and Risk Management Plan
MedDRA	Medical Dictionary For Regulatory Activities
NOA	Not analysed
NOR	No valid result
NOS	No sample available
PK	Pharmacokinetic(s)
PKS	Pharmacokinetic set
Q1	Lower Quartile
Q3	Upper Quartile
RAGe	Report appendix generator
REP	Residual effect period
RPM	Report Planning Meeting
SAE	Serious adverse event
SD	Standard Deviation

Term	Definition / description
SOC	System Organ Class
TS	Treated set
TSAP	Trial Statistical Analysis Plan
ULN	Upper limit of normal

3. INTRODUCTION

As per ICH E9 ([1](#)), the purpose of this document is to provide a more technical and detailed elaboration of the principal features of the analysis described in the CTP, and to include detailed procedures for executing the statistical analysis of the primary and secondary variables and other data.

This TSAP assumes familiarity with the CTP. In particular, the TSAP is based on the planned analysis specification as written in CTP Section 7 "Statistical Methods and Determination of Sample Size". Therefore, TSAP readers may consult the CTP for more background information on the study, e.g., on study objectives, study design and population, treatments, definition of measurements and variables, planning of sample size, randomisation.

Study data will be stored in a trial database within the Medidata Rave system.

The statistical analyses will be performed within the validated working environment CARE, including SASTM (current Version 9.4, by SAS Institute Inc., Cary, NC, USA), and a number of SASTM-based tools (e.g., macros for the analyses of AE data or laboratory data; Report Appendix Generator system (RAGe) for compilation/formatting of the CTR appendices).

PK parameters will be calculated using Phoenix WinNonlinTM software (version Phoenix 6.3, Certara USA Inc., Princeton, NJ, USA).

4. CHANGES IN THE PLANNED ANALYSIS OF THE STUDY

All analyses described in this TSAP are in accordance with the statistical methods described in the CTP.

5. ENDPOINTS

5.3 FURTHER ENDPOINTS

5.3.2 Safety parameters

Further safety parameters of interest will be used as defined in Section 2.2.2.2 of the CTP:

CTP:

- *Adverse events (including clinically relevant findings from the physical examination)*
- *Safety laboratory tests*
- *12-lead ECG*
- *Vital signs (blood pressure, pulse rate)*

6. GENERAL ANALYSIS DEFINITIONS

6.1 TREATMENTS

For basic study information on treatments to be administered, assignments of dose groups, and selection of doses, cf. Section 4 of the CTP.

All subjects were planned to be treated with

- one non-radiolabelled film-coated tablet of 50 mg BI 730357 on Day 1 and
- a single iv infusion of the microtracer 100 µg BI 730357 BS (C-14) on Day 1

The microtracer (reference treatment) will be administered starting 1.25 h after the administration of the table (test treatment) as a constant intravenous infusion over 15 min.

For statistical analysis of AEs, safety laboratory data and vital signs, the following analysis phases are defined for each subject:

Table 6.1: 1 Flow chart of analysis phases for statistical analyses of AEs, safety laboratory data and vital signs

Study analysis phase	Label	Start (inclusive)	End (exclusive)
Screening	Screening	Date of informed consent	Date/time of first administration of BI 730357
On-treatment	BI 730357	Date/time of first administration of BI 730357	Date/time of last administration of BI 730357 + REP (7 * 24 h)
Follow-up	F/U BI 730357	Date/time of last administration of BI 730357 + REP (7 * 24 h)	12:00 a.m. on day after subject's trial termination date

It will not be differentiated between intravenous or oral administration of the drug.

CTR Section 15, Appendix 16.1.13.1.8.2 and Appendix 16.1.13.1.8.3 AE displays will present results for the on-treatment phase only.

CTR Appendix 16.1.13.1.8.1 displays will present results for the screening, on-treatment and follow-up phases. Additionally to the following total will be provided in CTR Section 16.1.13.1.8.1 AE tables:

- "Total", defined as the total over all study phases (screening + on-treatment + follow-up)

The following labels will be used for the comparison of treatments:

Table 6.1: 2 Overview of treatments for intra-individual comparison

Treatment	Short label
T BI 730357, tablet, 50 mg, qd	BI 50 mg tab
R BI 730357, 98 μ g + 2 μ g (C-14) BI 730357 in 10 ml solution	BI 100 ug iv

More details on the technical implementation of these analyses are provided in the ADS Plan of this TSAP.

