7.3.4 Safety analyses

Safety will be analysed based on the assessments described in Section [2.2.2.2](#). All treated subjects (TS, refer to Section [7.3](#)) will be included in the safety analysis. Safety analyses will be descriptive in nature and based on BI standards. No hypothesis testing is planned.

For all analyses, the treatment actually administered (= treatment at onset) to the subject will be used (any deviations from the randomised treatment will be discussed in the minutes of the Report Planning Meeting).

Treatments will be compared in a descriptive way. Tabulations of frequencies/proportions will be used to evaluate categorical (qualitative) data, and tabulations of descriptive statistics will be used to analyse continuous (quantitative) data.

Measurements (such as ECG, vital signs, or laboratory parameters) or AEs will be assigned to treatments (see Section [4.1](#)) based on the actual treatment at the planned time of the measurement or on the recorded time of AE onset (concept of treatment emergent AEs). Therefore, measurements planned or AEs recorded prior to first intake of trial medication will be assigned to the screening period, those between first trial medication intake (test treatment) and beginning of reference treatment will be assigned to the test treatment period. Those between the start of infusion until the end of REP (see Section [1.2.3](#)) will be assigned to the combined test/reference treatment period. Events occurring after the REP but prior to next intake or end of trial termination date will be assigned to 'follow-up'. These assignments including the corresponding time intervals will be defined in detail in the TSAP. Note that AEs occurring after the last per protocol contact but entered before final database lock will be reported to Pharmacovigilance only and will not be captured in the trial database.

Additionally, further treatment intervals (analysing treatments) may be defined in the TSAP in order to provide summary statistics for time intervals, such as combined treatments, on-treatment totals, or periods without treatment effects (such as screening and follow-up intervals).

Adverse events will be coded using the Medical Dictionary for Regulatory Activities (MedDRA). Frequency, severity, and causal relationship of AEs will be tabulated by treatment, system organ class, and preferred term. SAEs, AESIs (see Section [5.2.6.1](#)), and other significant AEs (according to ICH E3) will be listed separately.

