6.3 SUBJECT SETS ANALYSED

All entered subjects who received study medication will be included in the safety analysis and in the PK analysis depending on the availability of measurement values, and on their adherence to the CTP.

The following subject sets will be defined for statistical analysis:

- Treated set (TS):
This subject set includes all subjects who received at least one dose of study drug. This is the full analysis set population in the sense of ICH-E9 ([1](#)). It will be used for analysis of safety, demographic data and baseline characteristics.
- Pharmacokinetic parameter set (PKS):
This subject set includes all subjects in the TS who provide at least one primary PK

parameter that was not excluded because of protocol deviations relevant to the statistical evaluation of PK endpoints as defined in Section 7.3 of the CTP.

The discussion of all exceptional cases and problems and the decisions on the allocation of subjects to analysis sets will be made at latest at the RPM/DBLM.

Table 6.3: 1 Subject sets analysed

Class of endpoint	Subject set	
	TS	PKS
Disposition	X	
Exposure	X	
iPDs	X	
Demographic/baseline endpoints	X	
Safety parameters	X	
Primary PK endpoint		X
Further PK endpoints		X

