7.8.1 Adverse events

The analyses of AEs will be descriptive in nature. All analyses of AEs will be based on the number of subjects with AEs and not on the number of AEs.

For analysis, multiple AE occurrence data on the eCRF will be collapsed into one event provided that all of the following applies:

- All AE attributes are identical (lower level term, intensity, action taken, therapy required, seriousness, reason for seriousness, relationship, outcome, AESI)
- The occurrences were time-overlapping or time-adjacent (time-adjacency of two occurrences is given if the second occurrence started at most 1 hour after the first occurrence ended)

For further details on summarization of AE data, please refer to "Analysis and Presentation of Adverse Event Data from Clinical Trials" (7) and "Handling of missing and incomplete AE dates" (3).

The analysis of AEs will be based on the concept of treatment emergent AEs. That means that all AEs will be assigned to the screening or on-treatment phase as defined in [Section 6.1](#). AEs will be analysed based on actual treatments, as defined in [Table 6.1: 1](#).

An overall summary of AEs will be presented. This overall summary will comprise summary statistics for the class of other significant AEs according to ICH E3 (8) and for the class of AESIs.

CTP: *The following are considered as AESIs:*

Hepatic injury

A hepatic injury is defined by the following alterations of hepatic laboratory parameters:

- *An elevation of AST (aspartate transaminase) and/or ALT (alanine transaminase) ≥ 3 -fold ULN combined with an elevation of total bilirubin ≥ 2 -fold ULN measured in the same blood sample, or*
- *Aminotransferase (ALT, and/or AST) elevations ≥ 10 -fold ULN.*

The investigator had to classify on the eCRF whether an observed AE was an AESI or not.

According to ICH E3 (8), AEs classified as "other significant" need to be reported and will include those non-serious and non-significant AEs

- (i) which are marked haematological or other lab abnormalities, or
- (ii) which were reported with "action taken = discontinuation" or "action taken = reduced", or
- (iii) which lead to significant concomitant therapy as identified by the Clinical Monitor/Investigator at a Medical Quality Review Meeting.

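### Does the SAP's single on-treatment phase, in place of the protocol's two periods, call for a change to the safety analysis?

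*SAP*

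**What the plan says.** Protocol 7.3.4 sets out how AEs and safety measurements are attributed. Anything before the first intake belongs to screening. For the next interval, "those between first trial medication intake (test treatment) and beginning of reference treatment will be assigned to the test treatment period". The interval described as "Those between the start of infusion until the end of REP" goes to a combined test/reference period, and later events go to follow-up. The detailed definition of these assignments is left to the SAP. The protocol then says: "Additionally, further treatment intervals (analysing treatments) may be defined in the TSAP", and gives combined treatments and on-treatment totals as examples.

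SAP Table 6.1: 1 has three phases: screening, one on-treatment phase labelled BI 730357 (first administration to last administration plus 7 × 24 h), and follow-up. The text below the table adds: "It will not be differentiated between intravenous or oral administration of the drug". For CTR Section 15 and two of the appendices, "AE displays will present results for the on-treatment phase only". The remaining appendix adds screening, follow-up and an overall total. SAP Section 4 states: "All analyses described in this TSAP are in accordance with the statistical methods described in the CTP".

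**The concern.** The protocol's rule is prescriptive, and pooled intervals are offered as an addition to the two periods. The SAP keeps the pooled interval and drops the two periods. A reader who relies on SAP Section 4 would believe that the protocol rule had been applied.

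Two practical consequences could follow. An AE that starts between tablet and infusion can be due only to the tablet (or to procedures), yet the AE summaries would not set it apart. And the treated set is defined by "This subject set includes all subjects who received at least one dose of study drug", so a subject who took the tablet but never received the infusion would be counted in the same column as subjects who received both.

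A smaller wording point lies alongside. SAP 7.8.1 says "That means that all AEs will be assigned to the screening or on-treatment phase as defined in" SAP 6.1, although the table there also has a follow-up phase.

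**Working it through.** **Inputs**

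- Tablet at 0 h; infusion starts at 1.25 h and lasts 15 min (Protocol 3.1, 4.1.4, Flow Chart).
- REP: 7 days = 168 h (Protocol 1.2.3; SAP Table 6.1: 1).
- Scheduled safety assessments: Protocol Flow Chart. Day 1 tolerance for vital signs, ECG and laboratory tests: ±30 min (Protocol 6.1).
- Doses: 50 mg oral, 100 µg intravenous (Protocol 4.1.4).
- Subjects: 6 planned, at most 8 (Protocol 3.3).

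**Step 1: boundaries side by side**

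| | Protocol 7.3.4 | SAP Table 6.1: 1 |
|---|---|---|
| Start of on-treatment time | first intake | first administration |
| Internal cut | start of infusion | none |
| End of on-treatment time | end of REP | last administration + 168 h |

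The outer limits agree. Only the internal cut is missing.

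**Step 2: length of the merged interval**

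On-treatment time with the REP counted from the start of infusion = 1.25 + 168 = 169.25 h. Share before the infusion = 1.25 / 169.25 = 0.74%. Counted from the end of infusion, it is 1.25 / 169.5 = 0.74%.

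**Step 3: scheduled measurements**

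The only assessment planned between 0:00 and 1:15 is a PK sample at 1:00. The first safety assessments after the tablet are:

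- local tolerability at 1:45: 1.75 − 1.25 = 0.50 h after infusion start
- ECG at 2:00: 2.00 − 1.25 = 0.75 h after
- vital signs at 4:00: 4.00 − 1.25 = 2.75 h after
- laboratory at 24:00: 24.00 − 1.25 = 22.75 h after

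Taken 30 min early, the first ECG falls at 1.50 h, still after infusion start. Under the protocol rule all these measurements fall in the combined period, so their summaries are the same with or without the cut. Only AEs can be regrouped.

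**Step 4: AE incidence**

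AE tables count subjects. The pooled phase is exactly the union of the protocol's two periods, so a subject with an event in either one counts once on treatment under both documents. Overall on-treatment incidence does not move.

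**Step 5: what split columns would show**

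One column would cover 1.25 h and the other 168 h, a ratio of 168 / 1.25 = 134.4. The same subjects would be in both, and the second is by definition a combined period. That pair of columns cannot support a comparison of routes. The intravenous dose is 100 µg against 50,000 µg orally, a factor of 500, and Protocol 4.1.2 treats its exposure as negligible.

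**Step 6: can early events still be found?**

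Infusion start and end times are recorded (Protocol 4.1.4), AE onset times are recorded (Protocol 5.2.6.2.1), and individual values are listed (SAP 7). In 6 to 8 subjects, any AE before the infusion can be read off directly.

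**The case for a change.** The strongest case is textual, and it stands. The protocol leaves the SAP to detail its assignments, which does not extend to removing one, and it permits pooled intervals beside the two periods. SAP Section 4 should therefore have named the pooling. SAP 7.8.1 also still describes AE tables as being by treatment when only one on-treatment label exists.

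The claim that a prespecified rule was silently dropped goes too far. SAP 6.1 gives the pooling a sentence of its own, in a SAP finalised as the place where the intervals were to be defined, and on-treatment totals are a form the protocol foresaw. What is missing is a cross-reference.

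The tablet-only subject adds little. If one occurred among 7 or 8 treated subjects, that would be 1/7 = 14% or 1/8 = 12.5% of the denominator, which is not trivial. But the protocol ends its test period at the start of the infusion and gives no end for a subject who is never infused, so following it literally would not settle that case. Splitting the columns would need a rule found in neither document, and one column could then mix subjects observed for 1.25 h with a subject observed for 168 h. The single label is accurate for such a subject, who did receive BI 730357.

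The follow-up omission in SAP 7.8.1 is a slip: Table 6.1: 1 and the display descriptions below it include that phase.

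**Conclusion.** The discrepancy is real, but it does not call for a change to the plan. Pooling two intervals of very unequal length in a descriptive safety analysis without hypothesis tests is a reasonable choice, and the SAP states it. The effect is confined to how AEs with onset in 0.74% of on-treatment time are grouped in the AE displays. Laboratory, vital-sign and ECG data, overall on-treatment incidence and the primary PK analysis are untouched. Naming the pooling in SAP Section 4 and adding follow-up to the sentence in SAP 7.8.1 would tidy the record, but neither would alter a result or a conclusion.

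This rests on the planned timing of the infusion; a long delay would widen the window, though the recorded times would still identify the events. It also rests on the documents at hand: protocol version 1.0 and the SAP without the separate technical plan for its analysis datasets, which might define further intervals.
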